#### **Dosing:**

- **Patients NOT taking EIAEDs or other drugs known to inhibit or induce CYP3A4 or PgP:** The dose will be administered according to the criteria in Section 5.1.
- **Patients taking EIAEDs:** The dose will be administered according to criteria in Section 5.1.
- **Patients taking moderate CYP3A4 and/or PgP inhibitors:** The dose will be administered according to criteria in Section 5.1.

CONFIDENTIAL

This document and information is the property of the NYU School of Medicine and Langone Medical Center. Do not disclose or use except as authorized in writing by the study IND sponsor

Dose adjustments will be permitted based on safety findings or serum everolimus levels for patients on treatment for 3 or 4 weeks. A detailed explanation of permitted dose adjustments and the process that will be implemented are found in Section 5.3.1 Dose Adjustments.

### **5.3 Study Drug Administration**

Patients will be instructed to take the prescribed dose of everolimus (or no treatment in the comparison group) orally with a glass of water at regular intervals, and each taken dose should be at the same time in the morning after a light, nonfat breakfast. Body Surface Area (in m^2) should be calculated using the following formula where weight (W) is in kilograms and height (H) is in centimeters \*(Dubois and Dubois, 1916): BSA= (W 0.425 x H 0.725) x 0.007184. The dose will be 4.5 mg/m^2 once daily; adjust to attain trough concentrations of 5-15ng/ml and exceptions for patients taking EIAEDs based on section 5.1.

Subjects will take the medication as specified in Section 5.1.

Dietary habits around the time of everolimus intake should be as consistent as possible throughout the study, and in particular, on the day when sample is being taken for pharmacokinetic analysis.

**NOTE:** Everolimus should NOT be taken with grapefruit or Seville orange juice. Patients with taking drugs that inhibit or induce CYP3A4 /450 or P-glycoprotein (P-gp) will be identified and doses adjusted for those who are taking EIAEDs.

Patients will receive treatment with study drug for 7 to 21days or until the occurrence of unacceptable toxicity as defined by the patient or guardian, or if a Grade 3 or 4 Adverse Event occurs as defined by Common Terminology for Adverse Events (CTAE) v.4.0 occurs, or the investigator or patient decides that continuation is not in the best interest of the patient. Interruption for toxicity will lead to discontinuation of the medication.

Overall, safety data available from completed, controlled and uncontrolled studies indicate that everolimus is generally well tolerated at weekly or daily dose schedules. The safety profile is characterized by manageable adverse events (AEs). These AEs are generally reversible and non-cumulative.

#### **5.3.1 Management of specific toxicities:**

Overall, safety data available from completed, controlled and uncontrolled studies indicate that everolimus is generally well tolerated at weekly or daily dose schedules. The safety profile is characterized by manageable adverse events (AEs). These AEs are generally reversible and non-cumulative.

Adverse events most frequently observed with everolimus are rash, stomatitis/oral mucositis, non-infectious pneumonitis, fatigue, headache, anorexia, nausea, vomiting, diarrhea, and infections. Overall, the most frequently observed laboratory abnormalities include neutropenia, thrombocytopenia, hypercholesterolemia, and/or hypertriglyceridemia. The majority of these AEs have been of mild to moderate severity (NCI CTC grade 1-2). Recommendations for dose adjustments for non-hematologic and hematologic adverse events are summarized in Tables 3 and 4.

**Table 3: Dosing guidelines for Everolimus-related non-hematologic toxicities**

CONFIDENTIAL

This document and information is the property of the NYU School of Medicine and Langone Medical Center. Do not disclose or use except as authorized in writing by the study IND sponsor

Toxicity	Action
AST or ALT elevation	Maintain current dose level
Grade 1 (> ULN - 3.0 x ULN)	
Grade 2 (> 3.0 - 5.0 x ULN)	
AST or ALT elevation	Interrupt Everolimus administration until resolution to $\leq$ grade 1 (or $\leq$ grade 2 if baseline values were within the range of grade 2). If resolution occurs $\leq$ 7 days, Everolimus should be re-started at the dose level prior to interruption.
Grade 3 (> 5.0 - 20.0 ULN)*	If resolution takes $>$ 7 days, or if event recurs within 21 days, hold Everolimus until recovery to $\leq$ grade 1 or baseline grade/ value and reintroduce Everolimus at one dose level lower, if available.
AST or ALT elevation	Interrupt Everolimus administration until resolution to $\leq$ grade 1 (or $\leq$ grade 2 if baseline values were within the range of grade 2). If resolution occurs $\leq$ 7 days, Everolimus should be re-started at one dose level lower. If resolution takes $>$ 7 days, discontinue Everolimus.
Grade 4 (> 20 x ULN)*	
Recurrence of grade 4 after dose reduction or toxicity requiring Everolimus interruption for $>$ 21 days	Discontinue Everolimus.
Intolerable grade 2 mucositis, or grade 3 AE, except hyperglycemia or hypertriglyceridemia or hypercholesterolemia	Interrupt Everolimus administration until resolution to $\leq$ grade 1 or baseline grade / value. If resolution occurs within $\leq$ 7 days, Everolimus should be re-started at the dose level prior to interruption. If resolution takes $>$ 7 days, or if event recurs within 21 days, hold Everolimus until recovery to $\leq$ grade 1 or baseline grade/ value and reintroduce Everolimus at one dose level lower, if available. Patients will be withdrawn from the study if they fail to recover to $\square$ grade 1 or baseline grade / value within 21 days.
Any other grade 4	Hold Everolimus until recovery to grade $\square$ 1 or baseline value Reintroduce Everolimus at one dose level lower, if available.
Grade 3 or 4 clinical liver failure (asterixis or encephalopathy/coma)	Discontinue Everolimus
Recurrence of intolerable grade 2 mucositis or grade 3 event after dose reduction	Reduce dose to the next lower dose level, if available. The lowest possible dose level of Everolimus is 2.5 mg daily. Below this level, Everolimus must be discontinued.
Recurrence of grade 4 after dose reduction	Discontinue Everolimus
Any non-hematologic toxicity requiring Everolimus interruption for $>$ 21 days	Discontinue Everolimus

**Table 4: Dosing guidelines for Everolimus-related hematologic toxicities**

CONFIDENTIAL

This document and information is the property of the NYU School of Medicine and Langone Medical Center. Do not disclose or use except as authorized in writing by the study IND sponsor

Toxicity	Action
Grade 1 thrombocytopenia (platelets 0-75, $\geq 75 \times 10^9/L$ )	No action.
Grade 2 thrombocytopenia (platelets <75, $\geq 50 \times 10^9/L$ )	Temporary dose interruption until recovery to Grade $\leq 1$ . Re-initiate treatment at the same dose.
Grade 3 thrombocytopenia (platelets <50,) OR	Interrupt Everolimus until resolution to grade $\leq 1$ Re-initiate treatment at a lower dose.
Grade 4 thrombocytopenia (platelets < 25 $\times 10^9/L$ )	Interrupt Everolimus until recovery to grade $\leq 2$ . Then reintroduce Everolimus at the same dose.
Grade 3 neutropenia or anemia (neutrophil <1, $\geq 0.5 \times 10^9/L$ )	Interrupt Everolimus until recovery to grade $\leq 2$ . Then reintroduce Everolimus at a lower dose.
Grade 4 neutropenia or anemia	Interrupt Everolimus until recovery to grade $\leq 2$ . Then reintroduce Everolimus at a lower dose.
Febrile neutropenia	Interrupt Everolimus until resolution to grade 1 (or baseline value) and no fever. Reintroduce Everolimus at one dose level lower, if available.*
Recurrence of grade 3 toxicity after dose reduction	Reduce dose to the next lower dose level, if available. The lowest possible dose level of Everolimus is 5 mg every other day (2.5 mg daily). Below this level, Everolimus must be discontinued.
*Recurrence of grade 4 toxicity (including febrile neutropenia) after dose reduction	Discontinue Everolimus
*Any hematologic toxicity requiring Everolimus interruption for > 21 days	Discontinue Everolimus

CONFIDENTIAL

This document and information is the property of the NYU School of Medicine and Langone Medical Center. Do not disclose or use except as authorized in writing by the study IND sponsor

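### Table 4 prints platelet bounds that do not fit together (Grade 1 reads both 0–75 and ≥75; Grade 3 has no lower bound), and its restart instructions conflict with sections 4.4.1 and 5.3

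*Combined protocol and SAP*

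**What the plan says.** Section 5.3.1 sends the reader to the toxicity tables: "Recommendations for dose adjustments for non-hematologic and hematologic adverse events are summarized in Tables 3 and 4". For platelets (×10⁹/L), Table 4 reads as follows.

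- **Grade 1.** The cell begins "Grade 1 thrombocytopenia (platelets 0-75" and continues with ≥75. The action is none.
- **Grade 2.** The cell begins "Grade 2 thrombocytopenia (platelets <75" and adds ≥50. The action is "Temporary dose interruption until recovery to Grade" ≤1, then "Re-initiate treatment at the same dose".
- **Grade 3.** The cell reads "Grade 3 thrombocytopenia (platelets <50,) OR", with nothing after the comma. The drug is interrupted until Grade ≤1, then "Re-initiate treatment at a lower dose".
- **Grade 4.** The bound is <25. The drug is interrupted until Grade ≤2. "Then reintroduce Everolimus at the same dose" follows.

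Two other sections govern the same events. Section 4.4.1 withdraws any subject with a Grade 3 or 4 event. Section 5.3 ends treatment at a Grade 3 or 4 event and says that an interruption for toxicity becomes a discontinuation.

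**The concern.** A dosing table works only if a laboratory value leads to one row. Here the row that asks for no action prints a range covering the counts for which the next three rows order interruption, and the Grade 3 row is open at the bottom.

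The protocol itself treats platelets as relevant. Section 5.3.1 lists thrombocytopenia among the most frequent laboratory abnormalities, Table 6 carries hemorrhages as an important identified risk, and section 5.4 (Prior and Concomitant Therapy) asks patients to avoid drugs affecting coagulation or platelet adhesion for 14 days before surgery. All treated subjects are due for brain surgery within 7 to 21 days of starting drug.

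There is also a data consequence. Whether drug continues, pauses or stops sets the everolimus exposure when tissue is taken for S6 phosphorylation, a primary outcome. Grade 3 and 4 events also enlarge the cohorts in Table 2. Those rules cite CTAE, but Table 4 is the only place in the text that prints platelet bounds by grade.

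**Working it through.** No sample size, power or event rate is involved. The check assigns counts to every row whose printed bounds they meet, then sets the result beside sections 4.4.1 and 5.3.

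**Inputs (Table 4, ×10⁹/L)**

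| Row | Printed bounds | Action printed in that row |
|---|---|---|
| Grade 1 | 0–75 and ≥75 | none |
| Grade 2 | <75, ≥50 | interrupt to Grade ≤1, same dose |
| Grade 3 | <50, no lower bound | interrupt to Grade ≤1, lower dose |
| Grade 4 | <25 | interrupt to Grade ≤2, same dose |

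**Step 1: can both Grade 1 bounds hold together?** 0 ≤ x ≤ 75 and x ≥ 75 gives x = 75 only. The cell therefore contradicts itself, and a reader has to choose one bound.

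**Step 2: rows met under each choice**

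| Count | Grade 1 taken as 0–75 | Grade 1 taken as ≥75 |
|---|---|---|
| below 25 (e.g. 20) | Grades 1, 3, 4: three actions | Grades 3, 4: two actions as printed |
| 25 to 49 | Grades 1, 3: two actions | Grade 3 only |
| 50 to 74 (e.g. 60) | Grades 1, 2: two actions | Grade 2 only |
| 75 | Grade 1 | Grade 1 |
| above 75 | no row | Grade 1 |

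The choice of ≥75 removes the no-action conflict at every count below 75. The overlap below 25 is left under either choice.

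**Step 3: Grade 3 beside Grade 4.** As the rows read, Grade 4 has the looser recovery grade (≤2 against ≤1) and the higher restart dose (same against lower). Grade ≤2 would also admit counts of 50 to 74, where the Grade 2 row interrupts. However, the Grade 3 cell ends in OR directly above Grade 4. If the two grades share one action, Step 3 falls away and the overlap below 25 no longer changes what is done.

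**Step 4: Table 4 beside sections 4.4.1 and 5.3**

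| Count | Table 4 | Section 4.4.1 | Section 5.3 |
|---|---|---|---|
| below 50 (Grade 3 or 4) | interrupt, then restart | withdraw | treatment ends |
| 50 to 74 (Grade 2) | interrupt, then restart (or no action, if 0–75 is read) | silent | interruption becomes discontinuation |

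Below 50, the two sections leave no room for any Table 4 restart. At 50 to 74 they do not settle the matter: the Grade 1 row read as 0–75 continues drug, the Grade 2 row pauses it, and section 5.3 turns that pause into a permanent stop.

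**The case against.** The strongest reply is that this is a typing or text-extraction fault that no clinician would follow. The row is labelled Grade 1, the rows for Grades 2 to 4 follow it, CTAE v4.0 is the named standard, and the tables are called recommendations. Table 3 visibly has split rows and lost symbols, so the layout of Table 4 cannot be trusted either. Sections 4.4.1 and 5.3 also stop drug at Grade 3 or 4, which makes the restart text largely moot.

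Much of this stands. The layout argument is enough to withhold any claim about Grade 3 against Grade 4: the trailing OR, and the identical actions printed for Grade 3 and Grade 4 neutropenia or anemia, both point to a shared or shifted action cell. The practical exposure is also small. There are 9 treated subjects, entry requires platelets ≥100, and the surveillance schedule in section 6.5 lists one blood count between the start of drug and hospital discharge. That leaves little time to detect, interrupt, recover and restart before surgery.

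Two things do not yield. The 0–75 range and the empty Grade 3 bound lie inside cells, so a column that slipped by a row does not explain them. And sections 4.4.1 and 5.3 do not cure the table; they contradict its restart instructions and leave counts of 50 to 74 unresolved.

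**Conclusion.** The point holds in limited form. As the text reads, the Grade 1 cell contradicts itself, the Grade 3 row is open at the bottom, and Table 4 restarts drug where sections 4.4.1 and 5.3 end it. This should be corrected, but it is not a fault in the statistical design.

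Three stronger readings are tempting, and the documents do not support them.

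- *Every count below 75 meets conflicting actions.* That uses 0–75 and ignores ≥75 in the same cell. Under ≥75, only counts below 25 meet two rows.
- *Grade 4 is deliberately treated more leniently than Grade 3.* The OR after Grade 3 and the uncertain layout mean this cannot be established without the original table.
- *The lowest counts get the loosest instructions in the protocol.* Sections 4.4.1 and 5.3 withdraw the subject or end treatment at Grade 3 or 4.

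The documents give no thrombocytopenia rate for this population, so an expected number of affected subjects cannot be stated. Each treated subject is 1/9 = 11% of the treated group, so even one change in exposure at tissue sampling would be visible in the S6 comparison. If the original table prints sound bounds, that part of the point falls away and the conflict with sections 4.4.1 and 5.3 is what is left.

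**What to change.** 1. Check Table 4 against its original layout: the Grade 1 bounds, the missing Grade 3 lower bound, and which action belongs to Grade 3 and which to Grade 4.
2. Correct the bounds so that each platelet count falls in exactly one row.
3. Reconcile the Grade 2 to 4 thrombocytopenia actions with each other, with the withdrawal rule in section 4.4.1 and with the treatment-end and interruption rules in section 5.3, and state which text governs.

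Which clinical action is right is for the sponsor's clinical team. The cost is the correction of one table by amendment, with whatever cross-reference step 3 requires. No patients or procedures are added.

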### 5.3.1.1. Management of stomatitis / oral mucositis / mouth ulcers

Patients with a clinical history of stomatitis/mucositis/mouth ulcers and those with gastrointestinal morbidity associated with mouth/dental infections, irritation of esophageal mucosa e.g. gastroesophageal reflux disease (GERD) and pre-existing stomatitis/mucositis must be monitored even more closely. Patients should be instructed to report the first onset of buccal mucosa irritation/reddening to their study physician immediately.

Stomatitis/oral mucositis/mouth ulcers due to everolimus should be treated using local supportive care. Please note that investigators in earlier trials have described the oral toxicities associated with everolimus as mouth ulcers, rather than mucositis or stomatitis. If your examination reveals mouth ulcers rather than a more general inflammation of the mouth, please classify the adverse event as such. We will follow the paradigm below for treatment of stomatitis/oral mucositis/mouth ulcers:

1. For mild toxicity (grade 1), use conservative measures such as non-alcoholic mouth wash or salt water (0.9%) mouth wash several times a day until resolution.
2. For more severe toxicity (grade 2) in which case patients have pain but are able to maintain adequate oral alimentation (see Table 5), manage with topical analgesic mouth treatments (i.e., local anesthetics such as, benzocaine, butyl aminobenzoate, tetracaine hydrochloride, menthol, or phenol) with or without topical corticosteroids, such as triamcinolone oral paste 0.1% (Kenalog in Orabase®). Temporarily interrupt dose until recovery to Grade ≤1. Re-initiate Afinitor® at the same dose. If stomatitis recurs at Grade 2, interrupt dose until recovery to Grade ≤1. Re-initiate Afinitor® at a lower dose.
3. For grade 3 in which case patients cannot maintain adequate oral alimenation, manage with topical analgesic mouth treatments (i.e., local anesthetics such as, benzocaine, butyl aminobenzoate, tetracaine hydrochloride, menthol, or phenol) with or without topical corticosteroids, such as triamcinolone oral paste 0.1% (Kenalog in Orabase®). Temporarily interrupt dose until recovery to Grade ≤1. Re-initiate Afinitor® at a lower dose.
4. For grade 4 in which symptoms are associated with life-threatening consequences, discontinue Afinitor and treat with appropriate medical therapy.
5. Agents containing alcohol, hydrogen peroxide, iodine, and thyme derivatives may tend to worsen mouth ulcers. It is preferable to avoid these agents.

**Table 5: Treatment for Patients with Intolerable Grade 2 Mucositis**

Intolerable grade 2 mucositis	Interrupt everolimus administration until resolution to ≤ grade 1 or baseline grade / value. If resolution occurs within ≤ 7 days, Everolimus should be restarted at the dose level prior to interruption. If resolution takes > 7 days, or if event recurs within 21 days, hold everolimus until recovery to ≤ grade 1 or baseline grade / value and reintroduce everolimus at one dose level lower, if available. Patients will be withdrawn from the study if they fail to recover to  grade 1 or baseline grade / value within 21 days.
-------------------------------	--

### 5.3.1.2. Management of skin toxicity

For patients with grade 1 toxicity, no specific supportive care is usually needed or indicated. Rash must be reported as an AE. Patients with grade 2 or higher toxicity may be treated with the following suggested supportive measures at the discretion of the investigator: oral minocycline, topical tetracycline, topical clindamycin, topical silver sulfadiazine, diphenhydramine, oral prednisolone (short course), topical corticosteroids, or pimecrolimus.

### 5.3.1.3. Management of diarrhea

CONFIDENTIAL

This document and information is the property of the NYU School of Medicine and Langone Medical Center. Do not disclose or use except as authorized in writing by the study IND sponsor

---

Appearance of grade 1-2 diarrhea attributed to study drug toxicity may be treated with supportive care such as loperamide, initiated at the earliest onset (for example 4 mg orally followed by 2 mg orally every 2 hours until resolution of diarrhea).

#### **5.3.1.4. Management of hyperlipidemia and hyperglycemia**

Treatment of hyperlipidemia should take into account the pre-treatment status and dietary habits of the patient. Grade 2 or higher hypercholesterolemia ( $>300$  mg/dL or  $7.75$  mmol/L) or grade 2 hypertriglyceridemia or higher ( $>2.5$  times upper normal limit) should be treated with a 3-hydroxy-3-methyl- glutaryl (HMG)-CoA reductase inhibitor (e.g. atorvastatin, pravastatin, fluvastatin) or appropriate triglyceride-lowering medication, in addition to diet.

Note: Concomitant therapy with fibrates and an HMG-CoA reductase inhibitor is associated with an increased risk of a rare but serious skeletal muscle toxicity manifested by rhabdomyolysis, markedly elevated creatine phosphokinase (CPK) levels and myoglobinuria, acute renal failure and sometimes death. The risk versus benefit of using this therapy should be determined for individual patients based on their risk of cardiovascular complications of hyperlipidemia.

Hyperglycemia has been reported in clinical trials. Monitoring of fasting serum glucose is recommended prior to the start of everolimus and periodically thereafter. Patients with diabetes mellitus will be excluded from the study.

#### **5.3.1.5 Management of infections**

Everolimus has immunosuppressive properties and may predispose patients to bacterial, fungal, viral or protozoal infections, including infections with opportunistic pathogens. Localized and systemic infections, including pneumonia, other bacterial infections, invasive fungal infections, such as aspergillosis or candidiasis and viral infections including reactivation of hepatitis B virus, have been described in patients taking everolimus. Some of these infections have been severe (e.g. leading to respiratory or hepatic failure) and occasionally have had a fatal outcome.

Physicians and patients should be aware of the increased risk of infection with everolimus. Treat pre-existing infections prior to starting treatment with everolimus. While taking everolimus, be vigilant for symptoms and signs of infection; if a diagnosis of infection is made, institute appropriate treatment promptly and consider interruption or discontinuation of everolimus.

If a diagnosis of invasive systemic fungal infection is made, discontinue everolimus and treat with appropriate antifungal therapy.

#### **5.3.2 Dose Adjustments**

There only planned dose adjustments will be in patients taking the drug for 3. Patients will be started on a set dose of everolimus based on their BSA ( $m^2$ ) and whether or not they are taking an EIAED. For those subjects taking everolimus for 3 weeks, a serum level will be obtained between days 10-12. If the result is in desired range (5-10 ng/ml) for patient receiving study medication, the recommendation will be no change. If the value is between 3-5 ng/ml, the dose will be increased by 2.0 mg/ $m^2$ /day and if the value is less than 3 ng/ml, the recommendation will be dose will be increased by 3.0 mg/  $m^2$ /day. If the value is between 10-13 ng/ml, the dose will be decreased by 2.0 mg/ $m^2$ /day. If the value is above 13 ng/ml, the dose will be decreased by 3.0 mg/ $m^2$ /day.

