#### **5.3.3 Serum drug levels**

The target range for everolimus serum levels in this study is between 5-10 mg/ml. For patients taking everolimus for 1 or 2 weeks, the only time an everolimus level will be assessed is on the morning of surgery from the reference laboratory. For those subjects taking everolimus for 3 weeks, a serum level will be obtained between days 10-12. All labwork will be performed at Tisch hospital, [name] or St Barnabas Medical Center [name] and the subjects taking everolimus for 3 weeks, the bloodwork will be done at the outpatient lab at Tisch Hospital as St Barnabas will only enroll controls

CONFIDENTIAL

This document and information is the property of the NYU School of Medicine and Langone Medical Center. Do not disclose or use except as authorized in writing by the study IND sponsor

---

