  - They will be instructed on the dosage and administration times of the study medication. All subjects will receive a specific quantity of tablets and they will be asked to record the time that each dose is given. They will be asked to bring back the medication that was not used so it can be reconciled with expected number of tablets to be used. This reconciliation will be logged on the drug reconciliation form, and signed and dated by the study team

6.2a Visit 2a – For patients taking the Everolimus for 3 weeks, at NYU CEC, they will have serum levels of everolimus drawn after 10-12 days on the medication. A trough level will be obtained. The study nurse or doctor will contact the patient with the results when available and will adjust the dose as described above. The nurse or doctor will also ask the patient to report any adverse events.

For active patients who reside outside of the NYC area and are unable to arrive at NYU CEC due to distance and travel issues prior to pre-admission testing, Visits 1 and 2 will be combined as one visit to be completed at least 7 days prior to Visit 3. For these patients with a combined Visit 1 and 2, this could mean a treatment window of 7-21 days depending both on which cohort they are in and how soon they can begin treatment.

Pre-surgical evaluation: Visit 2- Control Group

- Recent history will be reviewed for any change in medical status or change in intake of prescribed or over-the-counter medication.

CONFIDENTIAL

This document and information is the property of the NYU School of Medicine and Langone Medical Center. Do not disclose or use except as authorized in writing by the study IND sponsor

- Vital signs, physical and neurological examination
- A detailed seizure history during the prior week.
- Medication reconciliation.

Blood work: (pre surgical eval) CBC and C-reactive protein(CRP).

For control patients who reside outside of the NYC area and are unable to arrive at the study site due to distance and travel issues prior to pre-admission testing, Visits 1 and 2 will be combined as one visit and can be completed one day prior to Visit 3 if not earlier.

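### The everolimus trough target is 5–15 ng/ml in four sections, but the only adjustment rule with thresholds works to 5–10 and cuts the dose above 10 ng/ml

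*Combined protocol and SAP*

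**What the plan says.** **The 5–15 ng/ml target.** The Study Summary (patients not on enzyme-inducing antiepileptic drugs, EIAEDs) and Sections 1.5, 5.1 and 5.3 give a 4.5 mg/m² once-daily start, to be adjusted to a trough of 5–15 ng/ml.

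**The 5–10 target.** Section 5.3.2 gives the stepwise rule. It limits planned adjustments to one cohort: "There only planned dose adjustments will be in patients taking the drug for 3" (the word for weeks is missing, but the next sentences make it clear). For the day 10–12 level it says "If the result is in desired range (5-10 ng/ml) for patient receiving study medication, the recommendation will be no change". Above that range, "If the value is between 10-13 ng/ml, the dose will be decreased by 2.0 mg" per m² per day, and "If the value is above 13 ng/ml, the dose will be decreased by 3.0 mg" per m² per day. Section 5.3.3 states: "The target range for everolimus serum levels in this study is between 5-10 mg/ml". Sections 1.5 and 5.2 also give 5–10 for patients treated longer than two weeks, so Section 1.5 contains both ranges.

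**Who has a usable level.** At Visit 2a, for 3-week patients, "A trough level will be obtained" and the study nurse or doctor "will adjust the dose as described above". Section 5.3.3 adds: "For patients taking everolimus for 1 or 2 weeks, the only time an everolimus level will be assessed is on the morning of surgery".

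**Co-medication.** Section 5.1 halves the dose, approximately, for users of moderate CYP3A4 or PgP inhibitors and sets 5–10 ng/mL for them. It doubles the dose for EIAED users. For both groups it leaves later dosing to drug monitoring, without thresholds.

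**The concern.** A target range and the rule meant to reach it should have the same limits. Here the rule reduces the dose over part of the range that the target accepts. Staff working from Section 5.3 would leave a patient with a trough of 12 ng/ml alone. Staff working from Section 5.3.2 would reduce that patient's dose by 2.0 mg/m² per day. Both instructions cannot be followed.

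The level is acted on shortly before surgery, when tissue is taken for S6 phosphorylation, a primary outcome. Relating blood everolimus levels to brain S6 phosphorylation is a secondary objective in Section 2.2. Exposure at surgery in the 3-week cohort could therefore depend on which section was followed.

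**Working it through.** The plan derives no figure on this point, so the check compares the texts and then sizes the conflict.

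**Step 1: can the two ranges be reconciled?**

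| Possible explanation | What the text shows |
|---|---|
| 5–10 refers to a different kind of sample | Visit 2a makes the day 10–12 sample a trough, as in the 5–15 statements |
| 5–10 is the moderate-inhibitor range | Section 5.3.2 covers all 3-week patients and is not limited to that group |
| 5–10 is a deliberately narrower range for the 3-week cohort | Then 5–15 guides nobody on the standard dose: planned adjustments are confined to 3-week patients, and 1- and 2-week patients have a level only on the morning of surgery. Section 5.3.3 also states 5–10 for the study, not for a cohort |

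No explanation removes the conflict.

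**Step 2: which levels are affected.** Levels above 10 and up to 15 ng/ml are on target in four sections and reduced under Section 5.3.2. As a share of the range's width: (15 − 10)/(15 − 5) = 50%. This is not a share of patients, because the documents give no distribution of levels.

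**Step 3: size of the cuts.** The starting dose and its halving or doubling come from Section 5.1, the steps from Section 5.3.2.

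| Start (mg/m²) | Cut of 2.0 (10–13 ng/ml) | Cut of 3.0 (above 13 ng/ml) |
|---|---|---|
| 4.5 (standard) | 2.0/4.5 = 44%, leaves 2.5 | 3.0/4.5 = 67%, leaves 1.5 |
| 9.0 (doubled, EIAED) | 2.0/9.0 = 22%, leaves 7.0 | 3.0/9.0 = 33%, leaves 6.0 |
| 2.25 (halved, moderate inhibitor) | 2.0/2.25 = 89%, leaves 0.25 | 3.0 exceeds 2.25 |

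The last two rows apply only if the fixed steps cover those groups, which the protocol does not say.

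For illustration, assume that the level is proportional to dose (an assumption not in the documents). A standard-dose patient at 13 ng/ml given the larger cut would fall to 13 × 1.5/4.5 = 4.3 ng/ml, and one at 15 ng/ml to 15 × 1.5/4.5 = 5.0 ng/ml. That is at or below the lower limit of both ranges.

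**Step 4: would a cut show by surgery?** Section 1.5 gives about 150 h to equilibration.

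- Draw on day 12, surgery on day 21: (21 − 12) × 24 = 216 h, so 216 − 150 = 66 h to spare.
- Draw on day 10, surgery on day 21: (21 − 10) × 24 = 264 h, so 264 − 150 = 114 h to spare.
- Draw on day 12, surgery on day 15 (also longer than two weeks): (15 − 12) × 24 = 72 h, which is less than 150 h.

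In a 21-day course the cut would be fully reflected if the result is acted on within 66–114 h of the draw. Turnaround time is not given. In a shorter course it might not be.

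**Step 5: how many patients.** Table 2 lists 1–3 at 21 days. With 9 treated and at least 3 in each earlier cohort, 9 − 3 − 3 = 3 at most. The Section 5.2 text asks for 6, but 3 + 3 + 6 = 12 exceeds 9. If cohort 1 expands to the 9 that Table 2 lists after one event, 9 − 9 = 0 remain.

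**The case against.** The strongest reply is that the count is even. The 5–10 range appears in Sections 1.5, 5.2, 5.3.2 and 5.3.3, and wherever the protocol attaches a number to acting on the day 10–12 level, it is 5–10. Staff applying Section 5.3.2 have definite thresholds, and the 5–15 statements could be seen as general starting-dose wording. This is a fair account of how the rule would probably be applied. It does not remove the conflict, because the 5–15 statements are themselves instructions to adjust and Section 5.3 repeats one immediately before the rule.

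The second reply concerns reach, and it stands. The Study Summary says that enrolling patients 3–4 weeks before surgery has not been possible, so the 3-week cohort may be nearly empty. Section 1.5 expects starting doses often to need raising, which suggests that levels above 10 ng/ml may be uncommon.

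Third, no consequence for the results is shown. The S6 comparison sets treated patients across cohorts against controls, and the blood level at surgery is measured directly, so actual exposure will be known. This also stands and limits the weight of the point.

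**Conclusion.** The contradiction is real and lies in an operative dosing rule. Standard-dose 3-week patients with troughs above 10 and up to 15 ng/ml are on target in four sections and have the dose cut by 44% or 67% under Section 5.3.2. The point should be fixed, but its reach is small: 1–3 patients by Table 2, possibly none. These percentages assume the 4.5 mg/m² start with no EIAED or moderate inhibitor. No effect on S6 phosphorylation or safety is claimed.

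Two scope questions remain open:

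- Whether 5–15 ng/ml applies to EIAED patients. The Study Summary and Section 5.3 set them apart. Sections 1.5 and 5.1 change their dose but state no separate target.
- Whether the fixed steps apply to patients whose later dosing Section 5.1 individualizes.

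The ug/ml unit in Sections 1.5 and 5.2, the mg/ml unit in Section 5.3.3, and the pointer in Section 5.2 to 5.3.1 for dose adjustments are editorial slips.

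**What to change.** Reconcile the Study Summary and Sections 1.5, 5.1, 5.2, 5.3, 5.3.2 and 5.3.3 so that each dosing group (standard, EIAED, moderate inhibitor) has one stated target range in one unit. In Section 5.3.2, state which dosing groups the fixed steps cover and complete the sentence that limits planned adjustments to one cohort. Correct the pointer in Section 5.2. The choice of range and steps is for the sponsor's clinical team.

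The cost is protocol wording only, with no extra visits, samples or patients.
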